In our efforts to follow up on this latter work, we recently examined the error rates of alert and sleepy PI sufferers and normal sleepers across a series of simple and complex reaction time tasks. We employed age and gender matched samples of PI (N=89) sufferers and normal sleepers-NS (N=95). Participants underwent three nights of PSG followed by daytime testing with a four-trial Multiple Sleep Latency Test-MSLT. The PI and NS groups were each subdivided into "alert" (e.g., MSLT mean onset latency > 8 minutes) and "sleepy" (e.g., MSLT mean onset latency  $\leq$  8 minutes) subgroups to allow for testing the main and interaction effects of participant type and level of alertness. "Alert" participants had longer MSLT latencies than "sleepy" participants (12.7 vs. 5.4 minutes). PI sufferers had fewer correct responses on performance testing than did NS. However, as shown by the adjacent, figure we found a significant group x alertness interaction ( $p = .0013$ ) with greater error rates occurring among alert (hyperaroused) PI sufferers (Mean=4.5 $\pm$ 3.6 errors per trial) than among alert NS (Mean=2.6 $\pm$ 1.9 errors per trial). This was particularly true for the more complex switching attention task.

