## Study Design/Clinical Plan

- Provide a concise overview stating the type of experimental design

This study will use a matched-groups cross-sectional experimental design. Age and gender matched groups of hyperaroused PI sufferers and non-complaining normal sleepers (NS) will be recruited and enrolled. A comprehensive screening process that includes structured sleep and psychiatric interviews, screening questionnaires, vitals, urine pregnancy test, medical history, and diagnostic PSG will be used to determine eligible subjects. Our screening procedures and selection criteria are designed to allow us to identify and enroll hyperaroused PI sufferers and normally alert normal sleepers. PI sufferers enrolled will meet Research Diagnostic Criteria for insomnia disorder, score  $> 14$  on the Insomnia Severity Index, report insomnia for  $> 3$  months, have sleep difficulties  $\geq 3$  nights per week, score  $\leq 3$  on the Epworth Sleepiness Scale (ESS), score  $\geq 29$  on the Hyperarousal Scale and report an inability to nap in the daytime. The normal sleepers enrolled will report general satisfaction with sleep and no sleep/wake complaints, score  $\leq 10$  on the ESS, score  $< 25$  on the Hyperarousal Scale, and deny a practice of routine daytime napping. Those excluded will have: (a) a sleep-disruptive medical condition (e.g., rheumatoid arthritis); (b) a current major psychiatric (Axis I) condition on the basis of a Structured Clinical Interview for Psychiatric Disorders (SCID); (c) sedative hypnotic dependence and unwillingness/inability to abstain from these medications while in the study; (d) use of anxiolytics, antidepressants, or any other psychotropic medication; or (e) an apnea/hypopnea index (AHI)  $> 5$  or a periodic limb movement-related arousal index  $> 15$  during on screening PSG that includes a full sleep montage to allow for detection/diagnosis of sleep-disordered breathing and PLMD. Additionally, self-described NS who meet criteria for any sleep disorder and those insomnia sufferers who meet criteria for a comorbid sleep disorder in addition to PI will also be excluded.

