Following each administration of the performance testing, the participant will be placed in a laboratory bedroom for the MSLT trial. Most aspects of the standard protocol will be followed in conducting the MSLT. However, conservative MSLT criteria rather than contemporary clinical criteria will be used to define the sleep latency for each nap. Specifically, sleep latency will be defined as the time between the beginning of the nap trial and either the first three consecutive 30-second epochs of stage 1 sleep or the first 30-second epoch of any other sleep stage. If no sleep occurs, the trial will end at 20 minutes and a sleep latency of 20 minutes will be assigned. To minimize carry-over effects from one nap to the next, each nap trial will be discontinued 5 minutes after the sleep onset criterion is met.

Once all participants have completed the study protocol we will compare our groups of PI and NS in regard to their mean sleep onset latencies shown on the four MSLT naps to assure the groups do not differ in regard to their observed levels of daytime alertness. The dependent measures we plan to use in study analyses include: (1) mean reaction time per trial for each test; (2) # of correct responses per trial for each test; (3) # of errors of commission per trial for each test; (4) # of errors of omission per trial for each test; and (5) total # of errors per trial for each test. Our analysis plan below outlines how these measures will be used to test our study aims and hypotheses.

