# A

factorial analysis. Although our statistical model could also include "trials" as a factor, we have chosen to limit the complexity of our analyses by excluding this factor and using mean values of each of our performance measures across trials for each participant in our analyses. To further simplify our analyses we will compute mean values of our 5 dependent measures for the three simple tests and another set of mean values of these dependent measures for our three complex tests and use those composite means in all planned analyses.

Before conducting tests of the study hypotheses, we will conduct a number of preliminary 2 (PI vs. NS) x 2 (alert vs. sleepy) x 2 (simple vs. complex test) ANOVAs and cross tabs analyses to determine if the various "cells" of our study include participants who do not differ significantly in terms of their mean ages, years of education, gender compositions and racial/ethnic compositions. If study "cells" are found to differ significantly on any of these variables, those variables will be used as covariates in statistical models designed to test study hypotheses. If study cells do not differ in regard to these variables we will use unadjusted statistical models to test study hypotheses.

For study hypotheses 1 & 2, we will conduct 2 (PI vs. NS) x 2 (simple vs. complex test) MANOVAs/MANCOVAs analyses to test for statistical significance across the multiple performance measures derived from the neuro-cognitive test battery. If the MANCOVA/MANOVA shows significant results, univariate ANCOVAs/ANOVAs will be conducted to tests for similar significant effects for each individual performance measure (i.e., mean reaction time; within subject standard deviations for reaction time; error responses).

Hypothesis 1 will be tested via examination of the main effect of the *group factor* (PI vs. NS) in these analyses. Findings showing significantly slower and more variable reaction times, fewer correct responses and higher error rates in the hyperaroused PI group will support this hypothesis. Elimination of these statistical differences in repeat analyses that use hyperarousal scale scores as a covariate will confirm the role of hyperarousal in explaining the observed group differences.

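### Covariates enter the Hypothesis 1 and 2 models only after a significance screen; they should be fixed in advance

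*Combined protocol and SAP*

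**What the plan says.** Under Study Design/Clinical Plan the design is non-randomised and matched on two variables: "Age and gender matched groups of hyperaroused PI sufferers and non-complaining normal sleepers (NS) will be recruited and enrolled". Neither the closeness of the matching nor its type (individual or frequency) is given.

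Under Statistical Plans, age, years of education, gender and race/ethnicity go through preliminary ANOVAs and cross-tabulations. "If study 'cells' are found to differ significantly on any of these variables, those variables will be used as covariates"; otherwise, "If study cells do not differ in regard to these variables we will use unadjusted statistical models to test study hypotheses". No alpha is stated for these preliminary tests. No covariate is fixed in advance for Hypotheses 1 and 2, apart from repeat analyses using the hyperarousal score, and no matched-pair analysis is described.

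The screen is specified as "2 (PI vs. NS) x 2 (alert vs. sleepy) x 2 (simple vs. complex test) ANOVAs". The hypothesis models have only two factors, group and test difficulty. The alert/sleepy split is defined only for the pilot sample in Background and Rationale: "The PI and NS groups were each subdivided into 'alert' (e.g., MSLT mean onset latency > 8 minutes". For the present study, "Our screening procedures and selection criteria are designed to allow us to identify and enroll hyperaroused PI sufferers and normally alert normal sleepers", and the MSLT latencies are compared "to assure the groups do not differ in regard to their observed levels of daytime alertness".

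**The concern.** There are three separate problems.

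1. **Matched variables.** Close matching makes a significant age or gender difference between the groups unlikely, so the rule tends to drop these two. If they predict performance, matching has taken their variance out of the group contrast while the unadjusted model leaves it in the error term. The Hypothesis 1 group test and the complex-task contrast then run below their nominal alpha and give up some power.

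2. **Unmatched variables.** Confounding depends on the size of an imbalance and on how strongly the variable predicts the outcome. A significance test of the imbalance depends on sample size and ignores prediction altogether. A non-significant education gap can still bias the group contrast.

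3. **The screen itself.** A participant's age or education cannot differ between simple and complex tests, so that factor has no meaning here. The alert/sleepy factor does not appear in the hypothesis models, and this study does not define it. Whether a covariate enters the confirmatory model can therefore turn on a factor unrelated to the hypothesis.

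**Working it through.** **Inputs.** From Power Considerations: 82 per group; alpha .05; reaction time 470.6 vs 420.8 msec, SD 112.1; correct responses 75.7 vs 77.5, SD 3.74; errors 4.46 vs 2.60, SD 3.45; complex latency 496.65 vs 438.14, SD 133.4; simple latency 247.9 vs 226.4, SD 66.8. Assumed, because the documents give no values: covariate R² (share of within-group outcome variance), the education gap, the screen alpha and the closeness of matching.

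**Step 1: the plan's own figures.** Two-sided noncentral t, 162 df, critical value 1.975, noncentrality d/√(2/82).

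| Measure | d | Power | Plan |
|---|---|---|---|
| Errors | 1.86/3.45 = .539 | .929 | .93 |
| Correct responses | 1.80/3.74 = .481 | .865 | .87 |
| Reaction time | 49.8/112.1 = .444 | .807 | .81 |
| Complex latency | 58.51/133.4 = .439 | .797 | .80 |
| Simple latency | 21.5/66.8 = .322 | .535 | .54 |

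These agree, so the sample size is not in question.

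**Step 2: matched age and gender.** Let k be the share of the variance of the covariate's group-mean difference that matching leaves (0 = exact matching, 1 = none). The unadjusted statistic has standard deviation s = √(1 − R² + kR²), so its noncentrality and critical value are both divided by s. Adjustment divides only the noncentrality, by √(1 − R²).

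For reaction time the noncentrality is .444/√(2/82) = 2.845. With k = 0:
- R² 5%: s = .9747 and the effective critical value is 1.975/.9747 = 2.026, giving alpha .044. Power is .813 unadjusted and .827 adjusted.
- R² 10%: s = .9487 and the effective critical value is 2.082, giving alpha .039. Power is .820 unadjusted and .846 adjusted.

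Complex-task power moves from .803 to .817 (R² 5%) and from .810 to .837 (R² 10%). With k = .5, alpha is .047 and .044. With R² = 0 or k = 1 it is .050 and nothing is lost.

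The Hypothesis 2 interaction is a within-person contrast. At R² 10% and an assumed correlation of .3 to .7 between simple and complex scores, its alpha is .050 if covariate effects are equal in msec and .045 to .047 if they are equal in SD units.

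**Step 3: the education screen.** As a two-group test at .05, the smallest significant realised gap is 1.975 × √(2/82) = .308 SD. A true .25 SD gap has noncentrality .25/√(2/82) = 1.601 and is detected with probability .36. For a screen alpha of .01, .10 or .20 the probability is .16, .48 or .63.

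**Step 4: the whole rule, simulated.** Reaction time, education R² 10%, exact matching on age and gender with R² 5% / 10%, 60,000 runs per setting:

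| Setting | Rule | Always adjusted |
|---|---|---|
| Type I error, .25 SD gap | .046 / .042 | .049–.050 |
| Power, no gap | .818 / .821 | .864 / .882 |
| Power, gap masks the effect | .762 / .766 | .858 / .877 |
| Power, gap exaggerates the effect | .874 / .881 (biased upward) | .858 / .878 |

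With a .25 SD gap the average bias under the rule is .033 SD: .033 × 112.1 = 3.7 msec, or 3.7/49.8 = 7% of the planned difference. Among samples that pass the screen it is about .05 SD, close to 5.7 msec. A realised .25 SD gap left unadjusted shifts the contrast by .25 × √.10 × 112.1 = 8.9 msec (18%). With education R² of 5% or 20%, and age and gender at 5%, average bias is 2.6 or 5.4 msec and type I error .045 or .052.

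**Step 5: the extra factors in the screen.** If each person's record is duplicated over simple and complex tests, the screen threshold falls to .217 SD, detection rises to 59% and average bias drops to about 1.5 msec; the plan does not say whether records would be duplicated. Under exact matching the group term retains age at most 1% of the time. Age enters through alertness or its interaction about 10% of the time if unrelated to alertness, and 40–56% if the correlation is .2 (assumed alert share 50–85%, no duplication).

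**The case against.** The best case for leaving the rule alone has four parts.

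- **No figure in the plan is wrong.** Under close matching, unadjusted reaction-time power is at or slightly above the stated .81. The loss is measured against a better model and not against what the plan promised. This stands. The exception is a masking education gap, where power falls to about .76.
- **The matched-covariate effect is small.** It is 1.4 points at R² 5% (.813 to .827) and 2.6 at R² 10% (.820 to .846), and zero if age and gender do not predict performance. The larger gaps come from education. This also stands, and every size depends on values the documents do not give.
- **Error control is not threatened.** Simulated type I error of the whole rule is .042 to .054, because the conservatism from matching partly offsets the residual confounding. This stands: the argument concerns power, residual bias and a model chosen from the data, not false positives.
- **The alert/sleepy factor could be built.** Every participant has a four-trial MSLT, and the 8-minute pilot cut is available. A looser screen would also admit covariates more often, which moves towards the recommended model. Both points are fair. But the plan does not say that the pilot cut applies, and admitting age because it differs by alertness is not a reasoned basis for adjusting a comparison of PI with NS.

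These calculations treat reaction time as a single outcome. They do not model the plan's MANOVA gate, which covers five measures and a within-person factor.

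**Conclusion.** The concern holds, as an improvement worth making and not as a flaw that invalidates the plan. The text is unambiguous that adjustment depends on a significance test, and the screen as written includes one factor on which demographics cannot vary and another that this study does not define. Those points need no assumptions.

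The sizes do. At modest R² the rule costs one to three points of Hypothesis 1 reaction-time power through age and gender alone. The cost is about five to six points if education explains a further 10% of variance with no gap, and about ten to eleven if a .25 SD education gap masks the effect. It also leaves about 7% of the planned reaction-time difference as average bias in that last configuration, or the same amount in the other direction if the gap exaggerates the effect. The Hypothesis 2 interaction is largely unaffected.

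**What to change.** Delete the significance-test rule and the three-factor screen. Pre-specify age (continuous), gender, years of education and race/ethnicity as covariates in the Hypothesis 1 and 2 models whatever the observed balance. If matching is individual, a matched-pair analysis with education and race/ethnicity as covariates would serve instead. State in advance how race/ethnicity will be grouped and whether covariate-by-difficulty terms enter the Hypothesis 2 model. Describe how closely the groups are matched, report baseline characteristics descriptively without tests, and keep the unadjusted model as a sensitivity analysis.

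The cost is a change of wording and a few of the 164 − 2 = 162 error degrees of freedom. The present rule already needs all four variables, so no new data are collected.

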# A

administered battery of reaction time tasks. The assessment protocol will start two to three hours after participants' respective morning rising times and will begin with a battery of the neuro-cognitive testing followed by an MSLT nap. Per standard MSLT procedures, the daytime testing will be scheduled so the four performance testing and sleepiness assessment trials occur two hours apart. All daytime testing will be conducted under the supervision of trained laboratory technologists. Immediately prior to initiating daytime testing, participants' electrodes worn for the previous night's PSG will be checked and readjusted if necessary. Participants will be supervised between trials to prevent unscheduled sleep episodes. PSG electrodes will be worn for the entire day of laboratory testing and will not be removed until after the final trial is completed. Once the fourth performance/MSLT trial is completed and electrodes are removed, the participant will be allowed to leave the laboratory.

The neuro-cognitive test battery will include a 38 minute battery of simple and complex tests selected from CANTAB® Tests made available from Cambridge Cognition. The simple and complex tests will be presented in alternating order to control for the effects of fatigue on subjects' test performances. Among the simple tasks will be the Simple Reaction Time Test, Big Circle/Little Circle Test and Choice Reaction Time Test. These tests all provide measures of reaction time and motor speed but involve minimal cognitive load. The more complex tests will include the Rapid Visual Information Processing Test, The Spatial Working Memory Test and the Attention Switching Test. These latter tests collectively assess reaction time, attention, concentration, memory, and executive function, and thus, involve more cognitive load making them more sensitive to the deficits PI patients manifest. Both the simple and complex tests provide measures of respondents' mean reaction times, variability in reaction times across stimulus presentations, counts of correct responses, and counts of errors of omission and commission. These data are provided for each respondent for each trial allowing for analyses of respondents performances on a trial x trial basis as well as their average performances across trials.

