## Statistical Plans

- Include justification for clinical sample size and primary hypothesis testing:

As noted above, our main dependent variables of interest will include: (1) mean reaction time per trial for each test; (2) # of correct responses per trial for each test; (3) # of errors of commission per trial for each test; (4) # of errors of omission per trial for each test; and (5) total # of errors per trial for each test. We will use these data to test Hypotheses 1-2 and to address our exploratory Aim which will examine the relationship between various nocturnal sleep measures and daytime performance scores. Our hypotheses testing will be accomplished using a 2 (PI vs. NS) x 2 (simple vs. complex test)

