## Power Considerations:

We conducted power calculations for the study proposed using data from our previous two studies that compared reaction time performances of PI and NS participants. From the archival data sets used for these studies we obtained estimates of mean response latencies (reaction times) correct response rates and error rates for PI and NS groups to estimate the sample size needed to test the 2 study hypotheses. All power calculations were conducted using the proc power procedures available in SAS, version 9.2.

Hypothesis 1 entails testing the simple main effect of group membership (PI vs. NS) on neuro-cognitive performance. As a proxy for global performances we used response latency, correct response rate and error rate data derived from our 2008 study and our above referenced pilot study. Those studies showed the following information in comparisons of our hyperaroused PI group and normally alert NS group.

Measure	PI group	NS group	Sample standard deviation
Mean response latency - msec	470.6	420.8	112.1
Mean # correct responses	75.7	77.5	3.74
Means # errors	4.46	2.60	3.45

Given these data and assuming  $\alpha = .05$ , and 82 subjects in each of these two groups we would have a .93 power to detect the predicted group differences in their mean error rates across trials, .87 power to detect the predicted differences in mean correct response rates, and .81 power to detect the predicted differences in mean reaction time latencies.

Hypothesis 2 entails testing the interaction term showing that difficult reaction time tasks will show significant differences between PI and NS whereas simple tests will not. Basically this analysis ultimately will entail a posteriori contrasts that show PI vs. NS group differences on complex tasks but not simple tasks. Again we used response latency data obtained from our 2008 study for conducting power analyses for this hypothesis. Those data showed the following mean group differences and group standard deviations for complex and simple tasks.

Measure	PI group	NS group	Sample standard deviation
Complex test response latency - msec	496.65	438.14	133.4
Simple test response latency - msec	247.9	226.4	66.8

Given these data and assuming  $\alpha = .05$ , and 82 subjects in each of these two groups we would have a .80 power to detect the predicted group differences on complex tasks but only .54 power to detect group differences on the simple tasks.

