On the basis of these calculations we will plan to enroll 82 hyperaroused PI sufferers and 82 NS in this study.

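### Test difficulty varies within person, but the Hypothesis 1 and 2 models name no repeated factor or person-level error term; run literally, Hypothesis 1 is anti-conservative and Hypothesis 2 loses power

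*Combined protocol and SAP*

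**What the plan says.** **Design.** The Study Design/Clinical Plan section describes one computer battery containing three simple and three complex tasks, repeated over four trials. "The simple and complex tests will be presented in alternating order", so each participant does both kinds. The Statistical Plans section then averages over trials and over tests. This leaves one simple composite and one complex composite per participant for each of the five performance measures.

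**Model.** The same section states: "Our hypotheses testing will be accomplished using a 2 (PI vs. NS) x 2 (simple vs. complex test" and, for the two hypotheses, "we will conduct 2 (PI vs. NS) x 2 (simple vs. complex test) MANOVAs/MANCOVAs analyses to test for statistical significance". Univariate ANOVAs or ANCOVAs follow if the multivariate test is significant. Hypothesis 1 is read from the group main effect and Hypothesis 2 from the group-by-difficulty interaction, the latter supported by follow-up group comparisons. No repeated factor, mixed model or person-level error term is named. Within-subject variation is mentioned only as an outcome (the reaction-time SD).

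**Balance check.** Before the hypothesis tests, a three-way layout (group, alert or sleepy, simple or complex) is used to see whether the participants in its cells differ in age, education, gender and race or ethnicity.

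**Power.** The Power Considerations section works with "82 subjects in each of these two groups" and two-group comparisons. For Hypothesis 2 it gives means and SDs for latency only: "Complex test response latency - msec 496.65 438.14 133.4" and "Simple test response latency - msec 247.9 226.4 66.8" (PI mean, NS mean, SD).

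**The concern.** A factorial with difficulty as one of two factors can be fitted in two ways. In a mixed layout, group is tested against variation between people, and the interaction against variation in each person's complex-minus-simple difference. In a between-cells layout, every composite is a separate independent row and one pooled error term serves both tests.

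Only the mixed layout suits this design. The plan's wording does not ask for it, and the balance check leans the other way. The simple and complex cells hold the same people, so comparing their ages or gender mix makes sense only if difficulty is thought to divide participants.

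At stake are the tests of both hypotheses, which err in opposite directions. Under the between-cells layout the standard error for the group effect is too small and that for the interaction is too large.

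**Working it through.** **Inputs.** From Power Considerations: 82 per group; alpha .05; complex-test latency 496.65 vs 438.14 msec, SD 133.4; simple-test latency 247.9 vs 226.4 msec, SD 66.8. Sidedness is not stated. I take it as two-sided, because the plan's powers reproduce only that way. Rho, the within-person correlation of the two composites, is not given, so I use 0, .3, .5 and .7. It cannot be backed out of the Hypothesis 1 latency SD of 112.1, because an equal-weight average of the two composites can have an SD of at most (133.4 + 66.8)/2 = 100.1.

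**Step 1: the plan's own figures.** Power is approximately Phi(delta / (SD × sqrt(2/82)) − 1.96).
- Complex: 58.51/20.83 = 2.81, power .80 (plan .80).
- Simple: 21.5/10.43 = 2.06, power .54 (plan .54).
- Hypothesis 1 errors, correct responses and latency: .93, .87 and .81 (plan .93, .87, .81).

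All reproduce. All are comparisons with one value per person, and none is a power for the interaction.

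**Step 2: variance ratios.** Let k = 2 × 133.4 × 66.8 / (133.4² + 66.8²) = 17,822.24/22,257.80 = .80. Relative to the variance that a between-cells analysis assumes:
- true variance of the group effect = 1 + rho × k
- true variance of the interaction = 1 − rho × k

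**Step 3: Hypothesis 1 type I error under the between-cells analysis.** 2 × [1 − Phi(1.96 / sqrt(1 + rho × k))].

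**Step 4: Hypothesis 2 power.** The interaction is 58.51 − 21.5 = 37.01 msec. The between-cells standard error is SE0 = sqrt((2/82) × 22,257.80) = 23.30. The true standard error is SE = 23.30 × sqrt(1 − rho × k). Ignoring the negligible opposite tail:
- between-cells power = 1 − Phi((1.96 × SE0 − 37.01)/SE)
- within-person power = 1 − Phi(1.96 − 37.01/SE)

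| rho | 1 + rho·k | H1 type I error, between-cells | True SE of interaction | H2 power, between-cells | H2 power, within-person |
|---|---|---|---|---|---|
| 0 | 1.00 | .05 | 23.30 | .36 | .36 |
| .3 | 1.24 | .078 | 20.31 | .33 | .45 |
| .5 | 1.40 | .098 | 18.04 | .32 | .54 |
| .7 | 1.56 | .117 | 15.45 | .29 | .67 |

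**Step 5: simulation check.** With 20,000 runs per setting, between-cells type I error for Hypothesis 1 was .079, .098 and .116 at rho .3, .5 and .7. The mixed analysis stayed between .049 and .051 at every rho tried. Simulated Hypothesis 2 power was .33, .32 and .29 between-cells, against .44, .53 and .66 mixed.

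**Step 6: the multivariate test.** The direction is the same, but the size depends on settings that the documents do not fix. At rho .3, .5 and .7, the between-cells omnibus group test rejected a true null at about .09, .13 and .17 with three outcomes correlated .4. With four outcomes correlated .3 the rates were about .11, .15–.18 and .20–.25, the ranges covering 2:1 and equal SDs.

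**The case against.** The best reply is that this is a missing label rather than a wrong model. The plan never says that the factorial is ordinary or between-subjects, and two-by-two factorial is common shorthand for a mixed design. The trials factor, which the authors considered and set aside, is plainly within-person and carries no repeated-measures label either. The power section counts people, not rows. A competent analyst could therefore fit the mixed model under the existing wording. The cells language belongs only to the preliminary three-way check, which includes an alert/sleepy factor that no hypothesis test uses.

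Most of this stands as a limit on the claim. A reader might infer that the plan commits itself to the wrong analysis; the text does not go that far. It leaves two analyses open, which can give different p-values for both hypotheses, and its one explicit use of difficulty as a grouping of participants favours the wrong one. That is more than missing detail.

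A reader might also infer that both headline conclusions rest wholly on faulty error terms. That is too strong:
- Hypothesis 1 is supported only by a pattern across several measures after a significant omnibus test. The inflated omnibus rate is therefore not the rate at which the hypothesis would be declared supported.
- Hypothesis 2 also needs follow-up PI versus NS comparisons. Run separately by test type, these have one row per person and are unaffected.

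Nor does the point make the stated powers wrong. They reproduce on their own inputs.

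**Conclusion.** The point holds in conditional form. The plan should have stated that difficulty is within-person and did not, and a literal between-cells run would mis-test both hypotheses whenever rho is positive. At rho = .5, latency type I error for the group effect roughly doubles, and power for the interaction falls by about .22.

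These sizes assume two-sided alpha .05, the plan's latency SDs, and an assumed rho. At rho = 0 there is neither inflation nor loss, although a correlation near zero is unlikely for the same person doing reaction-time tasks in one session. SDs by difficulty are given only for latency, so the inflation cannot be computed from the plan for correct responses or errors. The multivariate figures are illustrative.

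The error term is also only part of the Hypothesis 2 shortfall. The quoted .80 belongs to the complex-task contrast. Even with the within-person term, interaction power for latency reaches .80 only at rho of about .85 (required SE 37.01/2.80 = 13.2, so 1 − .80 × rho = (13.2/23.30)² = .32).

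**What to change.** State in Statistical Plans that group is a between-person factor and test difficulty a within-person factor. Analyse with a doubly multivariate repeated-measures MANOVA/MANCOVA, and follow up each measure with a repeated-measures ANOVA/ANCOVA or a mixed model with an unstructured 2 × 2 covariance for the two composites.

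Equivalently, keep one row per person: test Hypothesis 1 on the mean of the simple and complex composites, and Hypothesis 2 on complex minus simple. Run the follow-up group comparisons separately by test type. Remove simple versus complex from the baseline balance check, since those cells contain the same people.

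The cost is a few sentences and different code, with no new data or participants. All that is given up is apparent Hypothesis 1 power bought by the inflated error rate: with the plan's latency differences at rho = .5, simulated rejection was .89 between-cells against .83 in the mixed analysis.
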